12.2.3.6 **Cytology, Histology:** These techniques can be used to differentiate between partial responses (PR) and complete responses (CR) in rare cases (e.g., residual lesions in tumor types, such as germ cell tumors, where known residual benign tumors can remain).

Cytology should be obtained if an effusion appears or worsens during treatment when the measurable tumor has met criteria for response or stable disease.

12.2.3.7 **FDG-PET:** While FDG-PET response assessments need additional study, it is sometimes reasonable to incorporate the use of FDG-PET scanning to complement CT scanning in assessment of progression (particularly possible 'new' disease). New lesions on the basis of FDG-PET imaging can be identified according to the following algorithm:

- a. Negative FDG-PET at baseline, with a positive FDG-PET at follow-up is a sign of PD based on a new lesion.
- b. No FDG-PET at baseline and a positive FDG-PET at follow-up: If the positive FDG-PET at follow-up corresponds to a new site of disease confirmed by CT, this is PD. If the positive FDG-PET at follow-up is not confirmed as a new site of disease on CT, additional follow-up CT scans are needed to determine if there is truly progression occurring at that site (if so, the date of PD will be the date of the initial abnormal FDG-PET scan). If the positive FDG-PET at follow-up corresponds to a pre-existing site of disease on CT that is not progressing on the basis of the anatomic images, this is not PD.

Note: A 'positive' FDG-PET scan lesion means one that is FDG avid with an uptake greater than twice that of the surrounding tissue on the attenuation corrected image.

THIS PROTOCOL IS FOR RESEARCH PURPOSES ONLY, SEE PAGE 1 FOR USAGE POLICY

12.2.4 Response Criteria for Patients with Solid Tumor and Measurable Disease**12.2.4.1 Evaluation of Target Lesions****Complete Response (CR):**

Disappearance of all target and non-target lesions. Any pathological lymph nodes (whether target or non-target) must have reduction in short axis to <10 mm. If immunocytology is available, no disease must be detected by that methodology. Normalization of urinary catecholamines or other tumor markers if elevated at study enrollment (for patients with neuroblastoma).

Partial Response (PR):

At least a 30% decrease in the sum of the diameters of target lesions, taking as reference the baseline sum diameters

Progressive Disease (PD):

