Table 4: Overall Response for Patients with Neuroblastoma and Measurable Disease

CT/MRI	MIBG	Bone Scan	Bone Marrow	Catechol	Overall
PD	Any	Any	Any	Any	PD

Any	PD	Any	Any	Any	PD
Any	Any	PD	Any	Any	PD
Any	Any	Any	PD	Any	PD
SD	CR/PR/SD	Non-PD	Non-PD	Any	SD
PR	CR/PR	Non-PD	Non-PD	Any	PR
CR/PR	PR	Non-PD	Non-PD	Any	PR
CR	CR	Non-PD	Non-PD	Elevated	PR
CR	CR	CR	CR	Normal	CR

Table 5: Overall Response Evaluation for Neuroblastoma Patients and MIBG Positive Disease Only

If patients are enrolled without disease measurable by CT/MRI, any new or newly identified lesion by CT/MRI that occurs during therapy would be considered progressive disease.

MIBG	CT/MRI	Bone Scan	Bone Marrow	Catechol	Overall
PD	Any	Any	Any	Any	PD
Any	New Lesion	Any	Any	Any	PD
Any	Any	PD	Any	Any	PD
Any	Any	Any	PD	Any	PD
SD	No New Lesion	Non-PD	Non-PD	Any	SD
PR	No New Lesion	Non-PD	Non-PD	Any	PR
CR	No New Lesion	Non-PD	Non-PD	Elevated	PR
CR	No New Lesion	CR	CR	Normal	CR

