### 6.5. Efficacy Analyses

#### 6.5.1. Efficacy Analysis Variables

Definition of efficacy analysis variables are listed below:

- **Objective response rate (ORR)** is defined as the proportion of treated patients achieving a best overall response of partial response (PR) or complete response (CR) per Response Evaluation Criteria in Solid Tumors Version 1.1(RECIST v.1.1). Patients who do not have any postbaseline tumor response assessments for any reason are considered nonresponders and are included in the denominator when calculating the response rate.
- **Disease control rate (DCR)** is defined as the proportion of treated patients achieving a best overall response of CR, PR, or stable disease (SD) per RECIST v.1.1. Patients who do not have any postbaseline tumor response assessments for any reason are considered non-responders and are included in the denominator when calculating the response rate.
- **Duration of response (DOR)** is defined from the date of first documented CR or PR (responder) to the date of objective progression or the date of death due to any cause, whichever is earlier. If a responder is not known to have died or have objective progression, then the patient will be censored at the date of last evaluable tumor assessment.
- **Progression-free survival (PFS)** is defined as the time from the date of randomization until the date of radiographic documentation of progression (as defined by RECIST v. 1.1) based on investigator assessment or the date of death due to any cause, whichever is earlier. The censoring is taken in the following order:
  - If a patient does not have a baseline disease assessment, then the PFS time will be censored at the randomization date, regardless of whether or not objective progressive disease (PD) or death has been observed for the patient.
  - If a patient is not known to have died or have investigator-assessed PD as of the data-inclusion cut-off date for the analysis, the PFS time will be censored at the date of last postbaseline adequate radiological tumor assessment, or at the date of randomization if the patient does not have any postbaseline adequate radiological assessment.

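### Neuroblastoma response Tables 4 and 5 leave some responding patterns without an overall response: normal catecholamines after CR on imaging (both tables), and CT/MRI response with stable MIBG (Table 4 only)

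*Protocol*

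**What the plan says.** Protocol Sections 12.4.4 and 12.5.2 send neuroblastoma patients to Section 12.7 for their best response. The first of the two neuroblastoma tables there is headed "Table 4: Overall Response for Patients with Neuroblastoma and Measurable Disease"; the second, Table 5, covers those with MIBG-positive disease only. The columns of Table 4 are CT/MRI, MIBG, bone scan, marrow, catecholamines and overall response. Apart from the PD rows it has five:

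- For a patient who is stable on CT/MRI, the row reads "SD CR/PR/SD Non-PD Non-PD Any SD".
- For a partial response on CT/MRI with a response on MIBG, it reads "PR CR/PR Non-PD Non-PD Any PR".
- For a response on CT/MRI with a partial one on MIBG, it reads "CR/PR PR Non-PD Non-PD Any PR".
- For a complete response on both with raised catecholamines, it reads "CR CR Non-PD Non-PD Elevated PR".
- For a patient clear at every site, it reads "CR CR CR CR Normal CR".

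Table 5 has the same last two rows, with absence of a new CT/MRI lesion in place of the CT/MRI response. Neither table has a default, or an entry for a site not assessed or not involved.

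Three other rules bear on this:

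- Section 12.2.4.1 defines PR for target lesions as "At least a 30% decrease in the sum of the diameters of target lesions" from baseline.
- Table 1 in Section 12.7.1 gives PR for a target CR or PR when non-target disease is neither CR nor PD.
- SAP Section 6.5.1 counts in ORR the treated patients "achieving a best overall response of partial response (PR) or complete response (CR"), judged by RECIST 1.1. It does not mention Tables 4 and 5.

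**The concern.** A lookup table for response should give every assessed, non-progressing patient a class, and a better finding should never lead to a worse result. Table 4 fails on both counts, and Table 5 shares the second fault.

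The catecholamine entry works backwards. A patient who has cleared CT/MRI and MIBG but still has a bone scan short of CR is PR with elevated catecholamines and has no class once they are normal. A CT/MRI responder whose MIBG is stable also has no class in Table 4, although the mirror case, stable CT/MRI with an MIBG response, is classed as SD.

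At stake are best overall response and, depending on which rule governs, ORR and DCR. Section 8.3.2 triggers central review on CR, PR or prolonged SD, so a patient with no class might also not be sent for review.

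**Working it through.** **Inputs.** The rows are those of Tables 4 and 5. The levels without progression are:

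- CT/MRI: CR, PR, SD (3)
- MIBG: CR, PR, SD (3)
- bone scan: CR or neither CR nor PD (2)
- marrow: CR or SD (2, Section 12.5.1)
- catecholamines: normal or elevated (2)

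The middle bone-scan level is an assumption, because Sections 12.4 and 12.5 define no bone-scan categories; Section 12.2.4.2 offers the equivalent for non-target lesions. Non-PD is read as anything except PD. The plan states no figure of its own to reproduce.

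**Table 4.** There are 3 × 3 × 2 × 2 × 2 = 72 combinations without PD. Matching each to the printed rows leaves 19 without a row, and none matches two conflicting rows.

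- CT/MRI CR or PR with MIBG SD: 2 × 1 × 2 × 2 × 2 = 16.
- CT/MRI CR and MIBG CR, normal catecholamines, bone scan and marrow not both CR: 2 × 2 − 1 = 3.

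**Table 5.** With no new lesion there are 3 × 2 × 2 × 2 = 24 combinations. Three have no row, all of them MIBG CR with normal catecholamines and bone scan and marrow not both CR. The CT/MRI gap cannot arise, because these patients have no CT/MRI-measurable disease.

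**Effect of the central MIBG rule.** Section 12.4.3 requires marrow clearance for a central MIBG CR if marrow was involved at enrolment. For such patients, two of the three catecholamine cells (marrow SD) cannot occur on central review. Unmatched cells fall to 19 − 2 = 17 in Table 4 and 3 − 2 = 1 in Table 5. The remaining catecholamine cell is a bone scan not rated CR. A bone scan not done has no entry in either table.

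**Parallel rules in the protocol.**

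| Rule | Pattern | Class |
|---|---|---|
| Table 1 | Target CR, non-target neither CR nor PD | PR |
| CNS table, 12.6.7 | Target CR, non-target incomplete/stable, markers normal | PR |
| Table 4 | CT/MRI CR, MIBG CR, bone scan not CR, catecholamines normal | none |
| Table 1 | Target PR, non-target neither CR nor PD | PR |
| Table 4 | CT/MRI PR, MIBG SD | none |

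The last comparison reads stable MIBG as non-target disease that is neither CR nor PD.

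**Effect of one patient.** One patient moved to PR changes ORR by 1/n: 1/6 = 16.7 points, 1/12 = 8.3, 1/24 = 4.2, 1/29 = 3.4. These n are assumed cohort or Part A sizes. SAP Section 6.5.2 reports ORR by dose level, so the smaller n are the more relevant.

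**How many responders.** The adult single-agent ORRs in Protocol Section 2.3.2 run from 4% to 9.5%. If they carried over to children, Part A would have between 0.04 × 24 = 1.0 and 0.095 × 29 = 2.8 responders across all tumour types.

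**After the fix.** A row for CT/MRI CR or PR with MIBG SD fills 16 cells. Accepting any catecholamine level in the PR row fills the other 3 in Table 4 and all 3 in Table 5. Unmatched cells go from 19 to 0 and from 3 to 0.

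**The case against.** The strongest reply is that ORR may not depend on these tables. The SAP ties ORR to RECIST 1.1 and limits the best-response summary to disease assessable by RECIST 1.1. Under Table 1 the CT/MRI responder with stable MIBG is a PR and is counted. A reader might infer that these patients are lost from ORR; the documents do not establish that. The SAP's nonresponder rule covers only patients with no postbaseline assessment. This stands. Against it, Sections 12.4.4 and 12.5.2 route best response through Section 12.7, and Section 12.4.3 says central MIBG responses serve the efficacy endpoint. The two documents therefore do not point to one rule.

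A reader might also take 19 of 72 to mean that about a quarter of neuroblastoma patients go unclassified. It does not: cells are not equally likely, and the number of neuroblastoma patients is not given.

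Nor is a complete responder at every site with normal catecholamines left out; that patient is CR.

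Bone scan is not named in the Section 8.1 schedule, but neither are CT and MIBG, so that silence alone proves little. What stands is that the tables require a bone-scan rating and do not say what to do when there is none.

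Finally, escalation is complete and Part B enrols only CNS tumours, so any change mostly reclassifies patients already treated. That limits the effect but does not make the tables right.

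**Conclusion.** The tables are wrong as written in one respect and incomplete in another. In both, the catecholamine entry gives a class to the worse patient and none to the better; on central review this mainly concerns a bone scan not rated CR or not done. In Table 4 only, CT/MRI CR or PR with MIBG SD has no class, in conflict with Table 1 and the SAP's RECIST-based ORR.

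The protocol's best-response classification is affected either way. ORR is affected only if Tables 4 and 5 drive it, and then most clearly for the catecholamine gap, where PR is the natural class. If the stable-MIBG pattern were set to SD, ORR as coded from the tables would not change and only DCR would. Few patients are likely to be involved, though one can move a dose-level ORR by 8.3 to 16.7 points at n of 12 or 6. Efficacy is a secondary aim and descriptive (Section 11.5), so no power or error rate is touched.

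**What to change.** 1. In Tables 4 and 5, in the row giving PR after MIBG CR, change the catecholamine entry from *Elevated* to *Any*, and state that the CR row is applied first. Without that order, a patient clear at every site would match both rows.
2. In the CR rows, accept for bone scan and marrow either CR or not involved at baseline, and say how a scan not done is read. Table 1 already gives PR for a target CR with non-target disease not evaluated.
3. Add a Table 4 row for CT/MRI CR or PR with MIBG SD. Symmetry with the existing SD row suggests SD; Table 1 gives PR. The class must be reconciled with Table 1 and the SAP.
4. State in SAP Section 6.5.1 whether neuroblastoma ORR and DCR use Tables 4 and 5 or RECIST 1.1 alone.

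The cost is a few table cells and one SAP sentence, settled before the efficacy tables are produced. No new assessment is needed if baseline non-involvement can be documented from imaging and marrow results already on file; where there was no baseline bone scan, the table note must say how non-involvement is established.

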12.7.2 Duration of Response

Duration of overall response: The duration of overall response is measured from the time measurement criteria are met for CR or PR (whichever is first recorded) until the first date that recurrent or progressive disease is objectively documented (taking as reference for progressive disease the smallest measurements recorded since the treatment started). This will be described by descriptive measures of duration of response as opposed to standard time to event analysis.

The duration of overall CR is measured from the time measurement criteria are first met for CR until the first date that progressive disease is objectively documented.

Duration of stable disease: Stable disease is measured from the start of the treatment until the criteria for progression are met, taking as reference the smallest measurements recorded since the treatment started, including the baseline measurements. This will be described by descriptive measures of duration of stable disease as opposed to standard time to event analysis.

13.0 ADVERSE EVENT REPORTING REQUIREMENTS

Adverse event data collection and reporting which are required as part of every clinical trial, are done to ensure the safety of patients enrolled in the studies as well as those who will enroll in future studies using similar agents. Adverse events are reported in a routine manner at scheduled times during a trial. (Please follow directions for routine reporting provided in the Case Report Forms for this protocol). Additionally, certain adverse events must be reported in an expedited manner to allow for optimal monitoring of patient safety and care. The following sections provide information about expedited reporting.

Reporting requirements may include the following considerations: 1) whether the patient has received an investigational or commercial agent; 2) whether the adverse event is considered serious; 3) the grade (severity); and 4) whether or not hospitalization or prolongation of hospitalization was associated with the event.

An investigational agent is a protocol drug administered under an Investigational New Drug Application (IND). In some instances, the investigational agent may be available commercially, but is actually being tested for indications not included in the approved package label.

Commercial agents are those agents not provided under an IND but obtained instead from a commercial source. The NCI, rather than a commercial distributor, may on some occasions distribute commercial agents for a trial.

All CTCAE v 5.0 codable AEs are considered reportable for this study. For detailed AE reporting guidelines refer to the “NCI Guidelines for Investigators: Adverse Event Reporting Requirements for DCTD (CTEP and CIP) and DCP INDs and IDEs”: http://ctep.cancer.gov/protocolDevelopment/adverse_effects.htm.

13.1 Steps to Determine If an Adverse Event Is To Be Reported In an Expedited Manner

Step 1: Identify the type of adverse event using the NCI CTCAE version 5.0. All appropriate treatment areas should have access to a copy of the CTCAE version 5.0. A copy of the CTCAE version 5.0 can be downloaded from the CTEP web site http://ctep.cancer.gov/protocolDevelopment/electronic_applications/ctc.htm.

Step 2: Grade the adverse event using the NCI CTCAE.

Step 3: Review Table A in this section to determine if:

- the adverse event is considered serious;
- there are any protocol-specific requirements for expedited reporting of specific adverse events that require special monitoring;

Note: This includes all events that occur within 30 days of the last dose of protocol treatment. Any event that occurs more than 30 days after the last dose of treatment and is attributed as Related (possibly, probably, or definitely) to the agent(s) must also be reported according to the instructions in the table below. Attribution categories are as follows: Unrelated (Unrelated, Unlikely); Related (Possible, Probable, and Definite).

Table A: Phase 1 and Early Phase 2 Studies: Expedited Reporting Requirements for Adverse Events that Occur on Studies under an IND/IDE within 30 Days of the Last Administration of the Investigational Agent/Intervention ^{1,2}

FDA REPORTING REQUIREMENTS FOR SERIOUS ADVERSE EVENTS (21 CFR Part 312)

NOTE: Investigators **MUST** immediately report to the sponsor **ANY** Serious Adverse Events, whether or not they are considered related to the investigational agent(s)/intervention (21 CFR 312.64)

An adverse event is considered serious if it results in **ANY** of the following outcomes:

- 1) Death
- 2) A life-threatening adverse event
- 3) An adverse event that results in inpatient hospitalization or prolongation of existing hospitalization for ≥ 24 hours
- 4) A persistent or significant incapacity or substantial disruption of the ability to conduct normal life functions
- 5) A congenital anomaly/birth defect.
- 6) Important Medical Events (IME) that may not result in death, be life threatening, or require hospitalization may be considered serious when, based upon medical judgment, they may jeopardize the patient or subject and may require medical or surgical intervention to prevent one of the outcomes listed in this definition. (FDA, 21 CFR 312.32; ICH E2A and ICH E6).

ALL SERIOUS adverse events that meet the above criteria MUST be immediately reported via CTEP-AERS within the timeframes detailed in the table below.

Hospitalization	Grade 1 and Grade 2 Timeframes	Grade 3-5 Timeframes
Resulting in Hospitalization	24-Hour, 7 Calendar Days	24-Hour 5 Calendar Days
Not resulting in Hospitalization		

Expedited AE reporting timelines are defined as:

- “24-Hour; 5 Calendar Days” - The AE must initially be reported via CTEP-AERS within 24 hours of learning of the AE, followed by a complete expedited report within 5 calendar days of the initial 24-hour report.
- “24-Hour; 7 Calendar Days” - The AE must initially be reported via CTEP-AERS within 24 hours of learning of the AE, followed by a complete expedited report within 7 calendar days of the initial 24-hour report.

Important note: In the narrative of the CTEP-AERS Report, please provide an explanation of the investigator's opinion regarding the determination of seriousness and indicate whether the reported event(s) is related or unrelated to any protocol procedures aside from the investigational agent (e.g required observations in Table 8.1).

¹Serious adverse events that occur more than 30 days after the last administration of investigational agent/intervention and have an attribution of possible, probable, or definite require reporting as follows:

Expedited 24-hour notification followed by complete report within 5 calendar days for:

- All Grade 3, 4, and Grade 5 AEs

Expedited 24-hour notification followed by complete report within 7 calendar days for:

- Grade 1 and Grade 2 AEs resulting in hospitalization or prolongation of hospitalization

² For studies using PET or SPECT IND agents, the AE reporting period is limited to 10 radioactive half-lives, rounded UP to the nearest whole day, after the agent/intervention was last administered. Footnote “1” above applies after this reporting period.

Effective Date: May 5, 2011

- Any medical event that precipitates hospitalization (or prolongation of existing hospitalization) must be reported regardless of attribution and designation as expected or unexpected.

- Any adverse event that results in persistent or significant disabilities/incapacities, congenital anomalies, or birth defects or exposure to study drug through breastfeeding must be reported via CTEP-AERS if the event occurs following treatment with the study drug.
- Use the NCI protocol number and the protocol-specific patient ID provided during trial registration on all reports.

Additional Instructions or Exceptions to CTEP-AERS Expedited Reporting Requirements for Phase 1 Trials Utilizing an Agent under a CTEP-IND or Non-CTEP IND:

- Death due to progressive disease should be reported as Grade 5 “Disease progression” in the system organ class (SOC) “General disorders and administration site conditions”. Evidence that the death was a manifestation of underlying disease (e.g., radiological changes suggesting tumor growth or progression: clinical deterioration associated with a disease process) should be submitted.
- Any death occurring within 30 days of the last dose, regardless of attribution to the investigational agent/intervention requires expedited reporting within 24 hours.
- Any death that occurs more than 30 days after the last dose of treatment with an investigational agent which can be attributed as Related (possibly, probably, or definitely) to the agent and is not clearly due to progressive disease must be reported via CTEP-AERS for an agent under a CTEP or non-CTEP IND agent per the timelines outlined in the table above.
- Myelosuppression, (Grade 1 through Grade 4 adverse events as defined in the table below), does not require expedited reporting, unless it is associated with hospitalization.

Category	Adverse Events
INVESTIGATIONS	Platelet count decreased
INVESTIGATIONS	White blood cell decreased
INVESTIGATIONS	Neutrophil count decreased
INVESTIGATIONS	Lymphocyte count decreased
BLOOD/LYMPHATICS DISORDERS	Anemia

As referenced in the CTEP Adverse Events Reporting Requirements, an AE that resolves and then recurs during a subsequent cycle does not require CTEP-AERS reporting unless (1) the Grade increases; or (2) hospitalization is associated with the recurring AE.

13.2 When to Report an Event in an Expedited Manner

- Some adverse events require notification **within 24 hours** (refer to Table A) via the web at <http://ctep.cancer.gov> (email the ADVL1416 COG Study Assigned Research Coordinator within 24 hours of becoming aware of the event if the CTEP-AERS 24-Hour Notification web-based application is unavailable) and by telephone call to the Study Chair. Once internet connectivity is restored, a 24-hour notification phoned in must be entered electronically into CTEP-AERS by the original submitter at the site.
- When the adverse event requires expedited reporting, submit the report **within 5 or 7 calendar days** of learning of the event (refer to Table A).
- Expedited AE reporting for this study must only use CTEP-AERS (Adverse Event

THIS PROTOCOL IS FOR RESEARCH PURPOSES ONLY, SEE PAGE 1 FOR USAGE POLICY

Expedited Reporting System), accessed via the CTEP home page <https://eapps-ctep.nci.nih.gov/ctepaers>.

